6.3 SAFETY POPULATION

The safety population will include all patients enrolled in this study and received at least one IP. The safety data will be analyzed as treated using the safety population.

6.4 **PER-PROTOCOL POPULATION**

The Per-Protocol (PP) population will include all patients who retain the 2 IP inserted in Treatment 1 for the 28 days of the treatment period (complete the two cycles of IP insertion) and complete the 4 Week Follow-up Visit post removal of the 2nd IP of Treatment 1 without any significant protocol deviations. Protocol deviations will be determined prior to database lock.

6.5 **PHARMACOKINETIC EVALUABLE POPULATION**

The pharmacokinetic population will include all patients enrolled in this study and who have at least one plasma or urine pharmacokinetic concentration measurement post-IP insertion and for whom the IP is successfully removed at the scheduled Treatment 1 Day 14 visit.

6.6 **DATA COLLECTED BUT NOT ANALYZED**

The Investigator's signature will not be analyzed.

7.0 **PATIENT DISPOSITION**

The number and percentage of patients in 2 of the study populations (mITT and PP) will be summarized by treatment group and study center; the number of patients screened will be summarized overall by study center.

Screen-failure patients (i.e., patients screened but not randomized) and the associated reasons for failure to randomize will be presented in a patient listing. The number and percentage of patients who complete the study and who prematurely discontinue during the same period will be presented for each treatment group and pooled across treatment groups for the mITT and PP Population. The reasons for premature discontinuation from the study as recorded on the termination pages of the electronic case report form will be summarized (number and percentage) by treatment group for the mITT and PP Population. Furthermore, this summary table will be generated for cohort of mITT patients that receive Treatment 2. Associated patient listing containing information on reasons for premature study discontinuation will be generated.

8.0 DEMOGRAPHICS AND OTHER BASELINE CHARACTERISTICS

8.1 **DEMOGRAPHIC**

Demographic parameters (age; age group; race; ethnicity; sex, smoking status and dietary lifestyle), baseline characteristics (weight; height; and body mass index, calculated as weight $[kg]/(height [m])^2$), will be summarized descriptively by treatment group for the mITT and PP populations and for the cohort of mITT patients that received Treatment 2. Continuous variables will be summarized by number of patients and mean, SD, median, minimum, and maximum values. Categorical variables will be summarized by number and percentage of patients.

8.2 **DISEASE CHARACTERISTICS**

The following baseline disease information will be summarized as described for the demographic information, by treatment group for the mITT and PP populations and for the cohort of mITT patients that received Treatment 2:

- information on stratification factors baseline average pain score ≤ 5 vs. > 5),
- daily average 24-hour pain Numeric Rating Scale (NRS),
- daily average worst pain NRS,
- Pain Catastrophizing Scale (PCS) total score,
- daily average number of micturition episodes,
- daily average number of urgency episodes,
- daily average pre- and post-void bladder pain NRS, and
- result of pelvic examination at baseline.

8.3 **PAST MEDICAL HISTORY**

Abnormalities in patients' medical and surgical histories will be coded using the *Medical Dictionary for Regulatory Activities*, version 18.1 or newer. The number and percentage of patients with abnormalities in medical and surgical histories in each system organ class and preferred term will be summarized by treatment group for the mITT Population. No statistical comparisons will be performed.

9.0 PRIOR OR CONCOMITANT MEDICATION

Prior medication is defined as any medication taken before the date of the first IP insertion. *Concomitant medication* is defined as any medication taken on or after the date of first IP insertion. The WHO drug dictionary, version 2015 quarter 4 or newer, will be used to classify prior and concomitant medications by therapeutic class and drug name.

9.1 BLADDER PAIN MEDICATION

Daily bladder pain and rescue bladder pain medication is recorded in the bladder pain diary for the screening period and treatment period. Both prior and concomitant daily bladder pain medication will be coded by drug name and therapeutic class. The use of these prior and concomitant medications will be summarized by the number and percentage of patients in each treatment group for the mITT Population. If a patient took a specific medication multiple times or took multiple medications within a specific therapeutic class, that patient would be counted only once for the coded drug name or therapeutic class. Formulations (including salts, esters, etc.) containing the same active ingredient will be pooled under the coded drug name of the base compound.

Prior and concomitant rescue bladder pain medication will be similarly summarized.

The number of days a given patient took concomitant rescue bladder pain medication will be summarized by treatment group and overall for the mITT population.

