5.8.2 Qualification for Retreatment

Patients can request retreatment (Treatment 2) at any time from the Week 4 Follow-up clinic visit up through the Week 20 Follow-up clinic visit. A patient will be eligible to receive Treatment 2 (LiRIS 400 mg) only if all of the following criteria are met:

- completed Treatment 1 schedule of visits and procedures from the Week 4 Follow-up visit through qualification, in the opinion of the investigator
- negative urine dipstick reagent strip test (for leukocyte esterase and/or nitrites) and, in the investigator's opinion, patient is asymptomatic for a UTI on the day of study treatment
- negative urine pregnancy result (for patients that are child bearing potential) and are willing to continue using acceptable method of contraception
- Investigator continues to deem treatment is appropriate and no condition or situation exists which, in the investigator's opinion, puts the patient at significant risk from receiving treatment

6. **Response Measures and Summary of Data Collection Methods**

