| 17.0 | DATA HANDLING CONVENTIONS 17.1 Visit Time Windows 17.2 Derived Variables 17.2.1 Pain Data Derivations 17.2.2 Void Data Derivations 17.3 Repeated or Unscheduled Assessments of Safety Parameters 17.4 Missing Date of the Last Dose of Study Treatment 17.5 Missing Severity Assessment for Adverse Events 17.6 Missing Causal Relationship to Study Treatment for Adverse Events 17.7 Missing Date Information for Adverse Events 17.8 Missing Date Information for Prior or Concomitant Medications 17.8.1 Incomplete Start Date 17.9 Character Values of Clinical Laboratory Parameters | $ \begin{array}{cccccccccccccccccccccccccccccccccccc$ | |
| 18.0 | CHANGES TO ANALYSES SPECIFIED IN PROTOCOL | 45 | |
| 19.0 | REFERENCES | 46 | |

3.0 **LIST OF ABBREVIATIONS**

| AE | adverse event |
|--------|--|
| ANCOVA | analysis of covariance |
| LOCF | Last observation carried forward |
| CI | Confidence interval |
| CRF | case report form |
| CV | Coefficient of variation |
| eCRF | electronic case report form |
| EQ-5D | EuroQol EQ-5D-5L |
| GM | Geometric mean |
| HRQoL | Health related quality of life |
| IC | informed consent |
| IC/BPS | interstitial cystitis/bladder pain syndrome |
| ICPI | Interstitial Cystitis Problem Index |
| ICSI | Interstitial Cystitis Symptom Index |
| IL-1β | Interleukin-1 beta |
| ITT | intent to treat |
| IP | investigational Product |
| LiRIS | lidocaine-releasing intravesical system |
| LS | least squares |
| MedDRA | Medical Dictionary for Regulatory Activities |
| MCP-1 | Monocyte chemoattractant protein-1 |
| mITT | Modified intent to treat |
| NRS | Numeric Rating Scale |
| PD | pharmacodynamics |

| PID | patient identification |
|------|----------------------------------|
| РК | pharmacokinetics |
| РР | Per Protocol |
| PVR | post-void residual |
| QoL | Quality of life |
| RBC | red blood cell |
| SAE | serious adverse event |
| SAP | statistical analysis plan |
| SD | Standard deviation |
| TEAE | treatment-emergent adverse event |
| WBC | white blood cell |

4.0 **INTRODUCTION**

This statistical analysis plan (SAP) provides a more technical and detailed elaboration of the statistical analyses of the efficacy and safety data as outlined and/or specified in the final protocol of Study 201025-001 (version dated 20 January 2015) and the most recent amendment (Amendment 2 dated [28 April 2016]). Specifications of tables, figures, and data listings are contained in a separate document.

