Study 201025-001 is a phase 2 multicenter, randomized, double-blind, placebocontrolled, study to evaluate the safety and efficacy of the LiRIS 400 mg in female patients with interstitial cystitis (IC) with Hunner's lesions (HL). This study includes up to 2 treatments. To receive Treatment 1, patients will be randomized in a 2:1:1 ratio to 1 of 3 treatment groups receiving over a 28-day treatment period either:

Group 1: 2 consecutive LiRIS 400 mg (N = 38)

Group 2: 2 consecutive LiRIS Placebo (N = 19)

Group 3: LiRIS Placebo followed by LiRIS 400 mg (N = 19)

Patients who qualify for Treatment 2, will receive LiRIS 400 mg over a 14-day treatment period followed by 4 weeks of observation until exit. Patients will be stratified based on screening baseline pain score (≤ 5 or > 5).

The primary analysis will be conducted at the time when the last patient completes the primary timepoint that is Week 4 following removal of the Treatment 1 second investigational product (IP) removal. The final analysis will be conducted when all patients complete or exit the study. For each analysis timepoint all data available will be included in the analysis. The analyses outputs to be included will be the same for the primary and final analysis timepoints. The schedule of evaluations for Study 201025-001 is presented in Table 4–1. The double-blind treatment period starts with the first IP insertion and ends with the last assessment prior to Treatment 2 IP insertion or Exit visit in the Treatment 1 period.

Table 4–1.

Schedule of Evaluation for Study 201025-001

Table 4–1.

Schedule of Evaluation for Study 201025-001

27MAR2018 CSR 201025-001

Table 4–1.

Schedule of Evaluation for Study 201025-001

5.0 **OBJECTIVES**

The study objective is to evaluate the safety and efficacy of a 28-day period of continuous release of lidocaine inserted into the bladder utilizing 2 consecutive LiRIS 400 mg compared with placebo for the treatment and corresponding symptoms of IC with HL in female patients. The clinical hypotheses is that a 28-day period of continuous release of lidocaine inserted into the bladder utilizing two consecutive LiRIS 400 mg will have an acceptable safety profile and will be more efficacious than placebo for the treatment and corresponding symptoms of IC with HL in female patients.

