10.0 EXTENT OF EXPOSURE AND TREATMENT COMPLIANCE

In this study patients receive two insertions of IP in Treatment 1 and one insertion of IP in Treatment 2. Treatment 2 is provided if the patient makes a request and qualifies for re-treatment. A request for re-treatment can only be made 4-weeks after the second IP had been removed. Hence, what are relevant in this study would be the duration of each treatment period (Treatment 1 and 2), whether or not the insertion and removal of the IP was completed as per the instruction provided in the protocol and whether or not a patient completed the 14 days cycle for each inserted IP.

10.1 **EXTENT OF EXPOSURE (DURATION OF EFFECT)**

Treatment duration for each Treatment period (1 or 2) will be displayed by treatment groups as well as the cumulative study duration over the entire study period. For Treatment 1 period, the treatment duration could be thought of as duration of effect. The following formula will be used to derive treatment duration:

Cumulative treatment duration:

Cumulative duration = exit date – Date of Treatment 1 first IP insertion + 1

Treatment 1 duration:

exit date – Date of Treatment 1 first IP insertion + 1,

for patients that exit without receiving Treatment 2 or,

Date of Treatment 2 IP insertion - Date of Treatment 1 first IP insertion

Treatment 2 duration:

exit date – Date of Treatment 2 IP insertion + 1,

If the date of exit date is missing, the date of the last visit will be used.

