For the primary analysis, for patients that get two IP inserted during Treatment 1 period, the Week 4 Follow-up is counted from the 2nd IP removal time. In contrast, for patients that just received one IP before exiting the study, the Week 4 Follow-Up is counted from the IP removal date. Hence, for Treatment 1 period, Week 1 Follow-Up- Week 4 Follow-Up assessment are from last IP removal, whether or not a patient received one or two IPs.

For the primary analysis, for patients that have IP inserted, if there is no valid Week 4 Follow-Up NRS assessment and there is a valid Week 2 or 3 Follow-Up, weekly mean of the average daily bladder pain NRS, the Week 4 Follow-Up value will be imputed by the latest of the two values that is available (i.e., Week 2 or 3 Follow-Up). For the primary efficacy analysis, the null and the alternate hypothesis are as follows:

Null hypothesis: The mean change from baseline in average daily bladder pain NRS at Week 4 Follow-Up post IP removal is the same or worse for the treatment group that utilizes 2 consecutive LiRIS 400 mg compared to the treatment group that utilizes 2 consecutive LiRIS Placebo.

Alternative hypothesis: The mean change from baseline in average daily bladder pain NRS at Week 4 Follow-Up post IP removal is greater for the treatment group that utilizes 2 consecutive LiRIS 400 mg compared to the treatment group that utilizes 2 consecutive LiRIS Placebo.

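### Rescue medication is summarised as a raw count of days over a Treatment 1 period whose length varies with retreatment and dropout, so the descriptive comparison by arm can be distorted

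*SAP*

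**What the plan says.** SAP 9.1 states the measure: "The number of days a given patient took concomitant rescue bladder pain medication will be summarized by treatment group and overall", for the mITT population. It names no rate, percentage or common window. SAP 9.0 defines concomitant medication as "any medication taken on or after the date of first IP insertion", which gives a start only.

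The end has to be taken from elsewhere. SAP 9.1 ties the diary to screening and the treatment period. SAP 4.0 says "The double-blind treatment period starts with the first IP insertion and ends with the last assessment prior to Treatment 2 IP insertion" or the Exit visit, and SAP 17.2, which applies throughout the plan unless stated otherwise, closes Treatment period 1 at Treatment 2 insertion or at study exit.

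When that happens is partly the patient's choice. Protocol 5.8.2: "Patients can request retreatment (Treatment 2) at any time from the Week 4 Follow-up clinic visit", with Week 20 as the last opportunity. Protocol 5.6.2 lets the insertion follow up to 14 days after qualification.

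SAP 10.1 reports time separately: "Treatment duration for each Treatment period (1 or 2) will be displayed by treatment groups as well as the cumulative study duration". It adds: "For Treatment 1 period, the treatment duration could be thought of as duration of effect". It does not link these durations to rescue days.

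**The concern.** A count of days grows with the time over which it is taken. Here that time is not fixed by design. It stops early for a patient who asks for retreatment early, and SAP 10.1 itself treats its length as something close to an outcome. The count therefore mixes how often rescue was used with how long the patient went without retreatment or dropout.

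Protocol 4.5.3 calls these medications confounding and asks that their use be minimised. A reader of a pain trial will naturally turn to this table to see whether rescue use differed between arms. If one arm leaves Treatment 1 sooner, its count falls for that reason alone, and the contrast can look too small, too large or reversed.

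The table also says little about the days that matter most for the primary result. The 7 days behind the Week 4 value are between 7/182 = 4% and 7/56 = 12.5% of a completer's counted time.

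**Working it through.** The documents give no figure for rescue use, so there is none to reproduce.

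**Length of Treatment 1 for a completer, in days from first insertion** (Protocol 3, 5.6 and 5.8.2; SAP 5.0 and 17.2):
- retreated at Week 4 Follow-up: 28 + 28 = 56
- never retreated: 28 + 140 = 168
- qualified at Week 20, inserted 14 days later: 28 + 140 + 14 = 182

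**Assumptions.** Rescue rates, retreated fractions and timing are all assumed. Let f and g be the fractions retreated on two placebo and two LiRIS systems, all at follow-up week w, with a constant weekly rate in each arm and no dropout. Mean weeks observed are f(4 + w) + 24(1 − f) and g(4 + w) + 24(1 − g). The ratio of counts is the true rate ratio times the ratio of these two.

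| Retreated, placebo v LiRIS | Week | Weeks observed | Ratio if truth is 1.0 | Ratio if truth is 2.0 |
|---|---|---|---|---|
| 60% v 30% | 4 | 14.4 v 19.2 | 0.75 | 1.50 |
| 60% v 30% | 12 | 19.2 v 21.6 | 0.89 | 1.78 |
| 60% v 30% | 20 | 24 v 24 | 1.00 | 2.00 |
| 50% v 30% | 12 | 20 v 21.6 | 0.93 | 1.85 |
| 30% v 60% | 4 | 19.2 v 14.4 | 1.33 | 2.67 |
| 50% v 50% | 4 | 16 v 16 | 1.00 | 2.00 |

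**Reversal is possible at an extreme.** Take 0.20 rescue days per day on placebo, 0.15 on LiRIS, and 60% v 20% retreated, all at Week 4. Placebo: 0.20 × (0.4 × 168 + 0.6 × 56) = 0.20 × 100.8 = 20.2 days. LiRIS: 0.15 × (0.8 × 168 + 0.2 × 56) = 0.15 × 145.6 = 21.8 days.

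**Dropout acts the same way.** With no retreatment, 0.20 in both arms, and 20% v 5% leaving at day 42, placebo gives 0.20 × 142.8 = 28.6 days and LiRIS 0.20 × 161.7 = 32.3 days.

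**Can the SAP 10.1 durations repair it?** With constant rates, yes. For 60% v 30% at Week 4 and a true ratio of 2.0, (28.8/14.4)/(19.2/19.2) = 2.0. Now suppose instead that heavier users are the ones who retreat at Week 4, at h days per week against 1 for everyone else, in both arms:
- 60% v 30%, h = 2: counts 19.2/21.6 = 0.89; corrected by arm duration (19.2/14.4)/(21.6/19.2) = 1.19; over the common first 8 weeks 1.6/1.3 = 1.23.
- 60% v 30%, h = 4: counts 28.8/26.4 = 1.09; corrected 1.45; common 8 weeks 2.8/1.9 = 1.47.
- 80% v 40%, h = 2 to 4: corrected 1.33 to 1.76; common 8 weeks 1.29 to 1.55.

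The arm-level correction can thus fall slightly short or overshoot. A percentage of days over a common window does not depend on the retreatment mix.

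**The case against.** The strongest reply is that this is one descriptive line in a concomitant-medication section. No visible text makes rescue days an endpoint or tests them between arms, and SAP 10.1 shows duration by group, so an attentive reader can see unequal follow-up. This stands as a limit on weight. It does not remove the problem, because a summary by arm invites comparison and the durations give only the crude correction shown above.

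A reader of SAP 9.0 alone might infer that the count has no end at all. The documents do not support that: SAP 17.2 bounds Treatment period 1. Counting through Treatment 2 as well would give 98 to 224 days, but that is the less supported reading and is not used here. What remains is that the bounded period varies in length and the count is not divided by it.

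The larger ratios assume all retreatment at Week 4, the most extreme timing. At Week 12 the distortion is less than half as large, and at Week 20 it vanishes. The visible retreatment criteria contain no pain or rescue-use threshold, so a link with arm or rescue use is possible but assumed.

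Finally, parts of the efficacy sections are redacted, and SAP 4.0 notes: "Specifications of tables, figures, and data listings are contained in a separate document". A window or denominator may already exist there. The point therefore concerns the visible text only.

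**Conclusion.** The point holds as a minor one. As written, SAP 9.1 yields a count whose contrast between arms is undistorted over Treatment 1 only if the arms are balanced on retreatment and dropout, or if the imbalance leaves time observed equal. Under an assumed 60% v 30% split, the ratio of counts is 0.75 to 1.00 times the true ratio, depending on whether retreatment falls at Week 4 or Week 20; the reverse split pushes it the other way.

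Two stronger inferences are not supported. One is that placebo patients will retreat more, so that the table will understate a benefit: the documents do not say which arm will retreat more, and the direction is open. The other is that the primary result is affected: rescue days do not enter the ANCOVA, and no primary estimate, test or power figure changes.

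**What to change.** Keep the count in SAP 9.1 and add, by arm, each patient's percentage of observed days with rescue use:
- (a) From first insertion to Week 4 Follow-up, before any Treatment 2. Leave out the insertion and removal days that SAP 17.2.1 drops from the weekly pain means: on schedule, 3 + 3 + 2 = 8 of 56 days with two systems, or 3 + 2 = 5 of 42 with one.
- (b) In the 7-day window that supplied the primary value: Days 50 to 56, or Days 36 to 42 for patients with one system. Where SAP 11.1 says "the Week 4 Follow-Up value will be imputed by the latest of the two values that is available", use that Week 2 or Week 3 window.

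Define an observed day once, for numerator and denominator alike: a calendar day in the window while the patient is on study. Rescue entries completed by site staff (Protocol 6.5.18) should count. Days with a urinary tract infection, when pain scores are not collected (Protocol 6.5.12), should be kept in both or dropped from both.

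Report rescue use from Week 4 to the end of Treatment 1, and in Treatment 2, separately and per days observed, so that later data are not lost. If the table specifications already provide this, a cross-reference in SAP 9.1 is enough.

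The cost is SAP wording and one more descriptive table. The diary already dates each entry, and the rescue rules and the primary analysis stay as they are.

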9.2 MEDICATION OTHER THAN BLADDER PAIN MEDICATION

Medication other than bladder pain medication will be collected in the concomitant medication eCRF. For both prior and concomitant medication collected in the eCRF, the frequency and percentage of medications will be summarized for the base preferred (drug) name (WHODDE) with the same active ingredients by the Primary System Organ Class and Preferred Term of the MedDRA dictionary.

The clinical team will also identify pain medication recorded in the concomitant medication eCRF prior to data base lock. For these medications a prior and concomitant medication table will be similarly generated.

10.0 EXTENT OF EXPOSURE AND TREATMENT COMPLIANCE

In this study patients receive two insertions of IP in Treatment 1 and one insertion of IP in Treatment 2. Treatment 2 is provided if the patient makes a request and qualifies for re-treatment. A request for re-treatment can only be made 4-weeks after the second IP had been removed. Hence, what are relevant in this study would be the duration of each treatment period (Treatment 1 and 2), whether or not the insertion and removal of the IP was completed as per the instruction provided in the protocol and whether or not a patient completed the 14 days cycle for each inserted IP.

10.1 **EXTENT OF EXPOSURE (DURATION OF EFFECT)**

Treatment duration for each Treatment period (1 or 2) will be displayed by treatment groups as well as the cumulative study duration over the entire study period. For Treatment 1 period, the treatment duration could be thought of as duration of effect. The following formula will be used to derive treatment duration:

Cumulative treatment duration:

Cumulative duration = exit date – Date of Treatment 1 first IP insertion + 1

Treatment 1 duration:

exit date – Date of Treatment 1 first IP insertion + 1,

for patients that exit without receiving Treatment 2 or,

Date of Treatment 2 IP insertion - Date of Treatment 1 first IP insertion

Treatment 2 duration:

exit date – Date of Treatment 2 IP insertion + 1,

If the date of exit date is missing, the date of the last visit will be used.

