10.2 MEASUREMENT OF TREATMENT COMPLIANCE AND TOLERABILITY

In this study, compliance to the insertion and removal procedures outlined in the protocol is assessed by the investigator. This information is collected in the IP insertion and removal eCRFs. The information in these eCRFs will be summarized by treatment group for each treatment period. Furthermore, associated listing will be produced.

For patients that spontaneously abort the IP or ask the IP to be removed prior to the Day 14 post-IP insertion, a summary table of such events will be presented by treatment group and overall.

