The data derivations and definitions listed in this section are to be applied to all analyses described in this analysis plan, unless otherwise stated.

- In this study there are two treatment periods:
 - Treatment period 1: for patients that just receive treatment in the randomized and blinded phase of the trial, it covers the period from the first Treatment 1 IP insertion to study exit. In contrast, for patients that receive IP insertions in both the randomized phase of the study (Treatment 1) and the open label phase of the study (Treatment 2) it covers the period from first Treatment 1 IP insertion up to Treatment 2 IP insertion,
 - Treatment period 2: covers the period from Treatment 2 IP insertion to study exit.
- Study days for each treatment period X (X=1 or 2) will be calculated as:
 - Study day of Treatment X = visit date (day 1 of Treatment X) + 1.
- The baseline value of an assessment will be the last value recorded prior to the patient being inserted with first Treatment 1 IP on Day 1.
- Unless otherwise stated no imputation will be performed for missing data. All analyses will be based on the observed data.
- For analyses that are by stratification factor, actual stratification levels rather than randomization stratification levels will be used.
- Data will be pooled across the investigational sites.
- Descriptive statistics for continuous/ordinal data include the sample size (N), mean, standard deviation (SD), median, minimum (Min), and maximum (Max) and 95% confidence intervals.
- Summary statistics for categorical variables include sample size (N), frequency count (n), and percentage (%).

17.2.1 **Pain Data Derivations**

A pain assessment tool will be utilized in the study to capture the average daily pain and the daily worst pain scores on an electronic hand held device. Patients will be asked to rate their daily pain on a pain NRS consisting of an 11 point integer scale ranging from 0 for "no pain" to 10 for "worst pain imaginable". The pain assessment will continue every day up to and including the day prior to the Exit visit.

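### SAP 10.1 measures time to retreatment or exit; it is neither exposure (56 to 169 days on schedule for 28 days with a device in place) nor duration of effect

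*SAP*

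**What the plan says.** SAP 10.1 defines Treatment 1 duration in two ways. For a patient who leaves without retreatment it is exit date minus first insertion date, plus 1. For a retreated patient it is "Date of Treatment 2 IP insertion - Date of Treatment 1 first IP insertion". Treatment 2 duration runs from the Treatment 2 insertion to exit, plus 1. The one rule for an absent end date is: "If the date of exit date is missing, the date of the last visit will be used". The section then offers an interpretation: "For Treatment 1 period, the treatment duration could be thought of as duration of effect".

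Other passages bear on this:

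- SAP 10.0 lists three relevant things: the length of each treatment period, whether insertion and removal followed instructions, and "whether or not a patient completed the 14 days cycle for each inserted IP".
- SAP 10.2 covers the insertion and removal eCRFs: "The information in these eCRFs will be summarized by treatment group for each treatment period". It also plans a table of IPs expelled, or removed at the patient's request, before Day 14.
- SAP 17.2 defines Treatment period 1 for patients who are not retreated: "it covers the period from the first Treatment 1 IP insertion to study exit".
- SAP 4.0 says of the two planned analyses: "The analyses outputs to be included will be the same for the primary and final analysis timepoints". It also says that all data available at each analysis will be used.

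**The concern.** A table headed extent of exposure should show how long each patient had the product. Here the product is in the bladder for a fixed, dated interval, and the study objective concerns a 28-day period of continuous release. A duration that ignores removal follows the patient's retreatment and exit decisions instead. It can differ between arms with identical device time, and it can agree between patients whose device time differs by half.

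The duration-of-effect reading adds a second difficulty. Stopping observation is not the end of an effect, and a patient cannot be retreated until four weeks after the second removal. If the table were quoted as evidence of durability, early withdrawals would count as short effects whatever the reason for leaving, and Week 20 completers as effects that ended at exit.

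**Working it through.** **Inputs** (Day 0 = first insertion)

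- Protocol 5.6.1: first IP in place Day 0 to Day 14, second IP Day 14 to Day 28. Follow-up lasts 20 weeks after removal, with exit at the Week 20 visit if there is no Treatment 2.
- Protocol 5.6.2: Treatment 2 insertion from Week 4 to Week 20 Follow-up, which may be put back by up to 14 days. The IP stays in for 14 days, followed by 4 weeks of follow-up.
- SAP 10.1: the formulas described above.
- SAP 11.1, for one-IP patients: "for patients that just received one IP before exiting the study, the Week 4 Follow-Up is counted from the IP removal date".

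**The plan's own calendar.** Protocol Section 3 gives 28 weeks for Treatment 1 only: 4 + 4 + 20 = 28, reproduced. Its 36-week maximum reproduces as 4 + 4 + 20 + 2 + 2 + 4 = 36, which needs the 14-day reschedule. The 182-day case below therefore lies inside the plan's own limits.

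**Visit days.** Week 4 Follow-up = 28 + 28 = Day 56. Week 12 = 28 + 84 = Day 112. Week 20 = 28 + 140 = Day 168.

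**Device-days.** Treatment 1: (14 − 0) + (28 − 14) = 28. Treatment 2: 14.

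| Patient | SAP 10.1 formula | Result | Device-days |
|---|---|---|---|
| Retreated at Week 4 | 56 − 0 | 56 | 28 |
| Retreated at Week 20 | 168 − 0 | 168 | 28 |
| Week 20 completer, not retreated | 168 − 0 + 1 | 169 | 28 |
| Qualifies at Week 20, inserted 14 days later | 182 − 0 | 182 | 28 |
| Two IPs, exits on Day 42 | 42 − 0 + 1 | 43 | 28 |
| One IP removed Day 14, exits at its Week 4 Follow-up (14 + 28 = Day 42) | 42 − 0 + 1 | 43 | 14 |
| Treatment 2, on schedule | 14 + 28 + 1 | 43 | 14 |

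The ratio to device-days is 56/28 = 2.0 at the low end for retreated patients, 169/28 = 6.0 for a completer and 182/28 = 6.5 at the limit. Two patients who exit on Day 42 score the same, although one had half the device time of the other.

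**Effect on arm means.** Assume every patient keeps both IPs for 28 days and everyone not retreated completes Week 20. Each 10-point difference between arms in the share retreated then moves the mean by:

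- 0.10 × (169 − 56) = 11.3 days if retreatment is at Week 4;
- 0.10 × (169 − 112) = 5.7 days if at Week 12;
- 0.10 × (169 − 168) = 0.1 day if at Week 20.

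Device time is identical throughout.

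**As duration of effect.** The first 28 days of every on-schedule two-IP value are treatment. A retreated two-IP patient has a floor of 56 whatever the effect. Exit ends the duration with no censoring, so the Day 42 withdrawal above scores 43 with or without relief.

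**At the primary data cut.** Patients still in follow-up have no exit date. If the missing-exit-date rule is applied to them, one whose latest visit is Week 4 scores 56 + 1 = 57. A patient retreated that same day scores 56. The first has not ended; the second has.

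**The case against.** The strongest defence is that this is mostly a matter of labels. SAP 10.0 asks for the length of each treatment period, and 10.1 delivers it consistently with SAP 17.2. SAP 10.2 and the per-protocol counts show who lost an IP early or kept both. With a fixed 14-day dwell per IP, counts carry most of what a device-days table would show. Lidocaine sampling in all enrolled patients bears on drug exposure, and the active-device split by arm is fixed by design. The duration-of-effect sentence is tentative, and no visible test or endpoint rests on it.

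Much of that stands, and it limits the point to descriptive reporting. It does not make the 10.1 figure an exposure: counts of early removals and plasma concentrations are not days in place.

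Four stronger readings are tempting, and the documents do not support them:

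- **That the SAP ignores removal data.** SAP 10.2 summarizes the removal eCRFs, and SAP 12.1 and 17.2.1 use removal dates. SAP 4.0 places table specifications in a separate document, which may already contain dwell time.
- **That no durability analysis exists.** Time to retreatment may sit in SAP text that was removed.
- **That a patient retreated at Week 4 and one still unretreated generally score alike.** The 56 against 57 arises only at the primary cut, only for patients whose latest visit is Week 4, and only by inference from the missing-exit-date rule. At the final analysis an on-schedule completer scores 169 against 56.
- **That retreatment marks the end of effect.** The visible criteria in Protocol 5.8.2 require no return of pain.

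**Conclusion.** The point holds for the definition and interpretation in SAP 10.1. As written, the section reports observation time under an exposure heading: 56 to 169 days on schedule, or 182 with the reschedule, for 28 device-days in Treatment 1, and 43 for 14 in Treatment 2. The duration-of-effect reading is unsupported, because treatment days are included, retreatment has a built-in floor, and exit is not censored.

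The day counts assume visits on schedule. The arm-mean shifts rest on the further assumptions stated with them. The 57-against-56 comparison is conditional on extending the missing-exit-date rule to ongoing patients. If that was not intended, the visible SAP has no rule for them, and a sentence is needed either way.

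The primary efficacy analysis and the sample size do not change. The correction should be made because it is cheap and the present label invites misreading.

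**What to change.** 1. In SAP 10.1, define exposure as the sum over IPs of (removal or expulsion date − insertion date), shown by arm and treatment period, unless the separate table specifications already do this.
2. Relabel the present measure as time to retreatment or exit (observation time), and delete the duration-of-effect sentence.
3. State that patients still in follow-up at the primary analysis are censored at the data cut-off. If durability is to be reported and no removed section covers it, use Kaplan-Meier for time from last Treatment 1 removal to Treatment 2 insertion, censored at exit or at the cut-off. Call it time to retreatment. Say that retreatment does not prove loss of effect, that absence of retreatment does not prove continued effect, and that on schedule the curve cannot fall before Week 4. Show exit reasons by arm, since exit may be related to lack of effect.

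The cost is SAP wording and one or two descriptive tables, with no change to conduct. Insertion and removal dates are already used elsewhere in the SAP. The remaining assumption is that an expulsion date is recorded, which the SAP 10.2 table of IPs lost before Day 14 appears to need.
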